3.1.5 Pharmacokinetic Studies

Approximately 15% of the administered platinum is present in the systemic. The remaining 85% is rapidly distributed into tissues or eliminated in the urine. It does not cross blood brain barrier. Oxaliplatin has more than 90% irreversible plasma protein binding, primarily albumin and gamma globulin. It also binds irreversibly to erythrocytes. It has a rapid and extensive non-enzymatic (no cytochrome P450-mediated metabolism) biotransformation to reactive platinum complexes which are both active and inactive metabolites. It has a triphasic elimination with terminal half-time of 391 hours. The major elimination route of platinum and its metabolites is renal excretion (54% within 5 days). Renal clearance of ultrafilterable platinum is significantly related to glomerular filtration rate.

3.1.6 Pharmaceutical Data

Refer to the package insert.

3.2 Leucovorin Calcium (CF)

3.2.1 Background Drug Information

See the current leucovorin calcium Product Monograph for details and up to date information.

3.2.2 Chemical Structure

Leucovorin calcium (folinic acid) is a reduced form of folic acid.

3.2.3 Mechanism of Action

Leucovorin is used to enhance the activity of fluorouracil by binding to the enzyme thymidylate synthetase and decreasing intracellular levels of thymidylate.

3.2.4 *Human Toxicology*

Deaths from severe enterocolitis, diarrhea and dehydration have been reported in elderly or debilitated patients receiving leucovorin and fluorouracil. Seizures or syncope have been reported rarely, usually in combination with fluorouracil and in patients with cerebral metastases, although a causal relationship has not been confirmed. Immediate allergic reactions and anaphylaxis can occur. Diarrhea and mucositis are common in combination with fluorouracil. Hand-foot syndrome and myelosuppression also occur in this combination.

3.2.5 *Pharmacokinetic Studies*

It is rapidly and extensively converted to 5-methyltetrahydrofolate derivatives in the intestine prior to abruption. 5-methyltetrahydrofolate is an active metabolite and inactive metabolites are also formed. It rapidly absorbs with 97% absorption at a 25 mg dose. Leucovorin has a 35 – 45 % of plasma protein binding. It distributes to all tissues with maximum accumulation in liver and CSF. Leucovorin crosses the blood brain barrier. Volume of distribution is 3.2 L/kg. It is mainly eliminated in urine (80 – 90 %) and small amounts in feces. Elimination half-life is 32 min for parent drug and 227 min for active metabolite with a clearance of 3.9 mL/min/kg.

3.2.6 *Pharmaceutical Data*

Refer to the package insert.

3.3 *Fluorouracil*

3.3.1 *Background Drug Information*

See the current fluorouracil Product Monograph for details and up to date information.

3.3.2 *Fluorouracil Chemical Structure*

Its chemical name is 5-Fluoro-1H,3H-pyrimidine-2,4-dione, chemical formulae is C₄H₃FN₂O₂ with a molar mass of 130 g/mol.

3.3.3 *Mechanism of Action*

Fluorouracil was developed based on the observation that tumour cells utilized the base pair uracil for DNA synthesis more efficiently than did normal cells of the intestinal mucosa. It is a fluorinated pyrimidine antimetabolite that is metabolized intracellularly to its active form, fluorouridine monophosphate (FdUMP). The active form inhibits DNA synthesis by inhibiting thymidylate synthetase and the normal production of thymidine. Effects on RNA (incorporation into RNA and RNA inhibition) occur especially with bolus administration. Fluorouracil is cell cycle phase-specific (S-phase).

3.3.4 *Human Toxicology*

Following longer IV infusions, *mucositis, hand-foot syndrome and diarrhea* occur most commonly. Diarrhea may be profuse and life-threatening following administration of leucovorin with fluorouracil. *Leukopenia* is the usual dose-limiting toxicity after IV bolus administration

Patients with dihydropyrimidine dehydrogenase deficiency (DPD) are at risk of severe lifethreatening toxicity with fluorouracil. While severe deficiency is rare, 3-4% of the population has some degree of DPD deficiency.

Excessive lacrimation occurs frequently. Transient blurring of vision, eye irritation and excessive nasal discharge have also been reported. The onset of eye symptoms may occur at any time during treatment. Fluorouracil has been demonstrated in tear fluid causing acute and chronic conjunctivitis that can lead to tear duct fibrosis.

Acute cerebellar syndrome is manifested as ataxia of the trunk or extremities, disturbance of gait and speech, coarse nystagmus and dizziness. The ataxia syndrome is related to peak plasma levels of the drug rather than to cumulative dose, and is therefore more common with bolus doses than with infusions. It usually resolves after treatment is discontinued, but may persist in some cases.

Palmar-plantar erythrodysesthesia or hand-foot syndrome has been noted with protracted and high dose continuous infusion (23-82%). The syndrome begins with dysesthesias of the palms and soles that progress to pain and tenderness. There is associated symmetrical swelling and erythema of the hand and foot. The syndrome resolves gradually over 5 to 7 days with cessation of drug infusion.

Cardiotoxicity has been reported and may be caused by coronary vasospasm, endothelial cell damage or increased thrombogenicity. It occurs in less than 10% of patients, of which up to 8% may be fatal. Cardiac effects include ECG changes, angina, arrhythmias, myocardial infarction, heart failure and are usually reported within 72 h of the first cycle of fluorouracil. Cardiotoxicity is independent of dose or underlying cardiac risk factors, but may be more common with infusions. Patients should be rechallenged only when there are no other treatment options.

Fluorouracil has the potential to enhance radiation injury to tissues. While often called radiation recall reactions, the timing of the radiation may be before, concurrent with or even after the administration of the fluorouracil. Recurrent injury to a previously radiated site may occur weeks to months following radiation.

Hemolytic-uremic syndrome has been reported when used in combination with mitomycin C.

Brivudine, sorivudine or their chemically related analogues irreversibly inhibit DPD, resulting in a significant increase in fluorouracil exposure. This may lead to increased fluoropyrimidinerelated toxicities with potentially fatal outcome. Therefore, either a different antiviral therapy may be used or there should be an interval of at least 4 weeks between the administration of brivudine, sorivudine, or the analogues and the start of fluorouracil treatment. In the case of accidental administration of nucleoside analogues that inhibit DPD activity to patients treated with fluorouracil, effective measures should be taken to reduce fluorouracil toxicity. Immediate hospitalization is recommended.

Treatment with cimetidine for several weeks before initiation of fluorouracil treatment may increase plasma fluorouracil concentrations. This effect is probably due to both inhibition of hepatic enzymes and reduction of hepatic blood flow. Caution should be taken if the patient receives fluorouracil and cimetidine concurrently.

Metronidazole may enhance the toxicity of fluorouracil. The mechanism of interaction is presumed to be reduced clearance of fluorouracil by metronidazole. Concurrent administration should be avoided.

Elevated INR levels and occasional episodes of bleeding have been reported during concomitant use of warfarin and fluorouracil or its analogues. In these cases, fluorouracil has usually been administered as one component of an antineoplastic combination regimen. Adequate anticoagulant response to warfarin and other coumarin-derivative therapy should be monitored regularly in patients taking fluorouracil.

3.3.5 *Pharmacokinetic Studies*

Fluorouracil distributes into all body water by passive diffusion, crosses placenta and blood brain barrier, reaches high and persistent concentration in malignant effusions and has only 10% plasma protein binding. Eighty percent of the dose is degraded in liver by dihydropyrimidine dehydrogenase to active and inactive metabolites. It is mainly excreted as respiratory CO₂ (60 – 80 %), with 15 -20% excreted in the urine as intact drug within 6 hours after administration and 2-3% by biliary system. Higher clearance occurs in IV infusions than IV injections, due to saturation of metabolic or transport processes at higher drug concentrations. Elimination half-life is 6 – 20 mins dose dependent.

3.3.6 *Pharmaceutical Data*

Refer to the package insert.

3.4 *Capecitabine*

3.4.1 *Background Drug Information*

See the current capecitabine calcium Product Monograph for details and up to date information.

3.4.2 *Chemical Structure*

Capecitabine is an antimetabolite, belonging to the fluoropyrimidine carbamate class. The molecular formulae is C₁₅H₂₂FN₃O₆ and molecular weight is 359 g/mol.

3.4.3 *Mechanism of Action*

It causes cell injury via RNA- and DNA-related mechanisms. It is an orally administered precursor of 5- fluorouracil (5FU). Capecitabine is converted to 5FU by carboxyesterase, cytidine deaminase and thymidine phosphorylase (present in the liver and in tumours). Docetaxel appears to upregulate thymidine phosphorylase. The daily oral administration of capecitabine mimics the continuous intravenous infusion of 5-FU.

3.4.4 *Human Toxicology*

The most common side effects for capecitabine include hand-foot syndrome, diarrhea, nausea, vomiting, mucositis, abnormal liver function tests, fatigue, abdominal pain, anorexia, weight loss, edema and headache.

The median time to onset of diarrhea, a dose-limiting adverse effect of capecitabine, is 34 days. The diarrhea may respond to standard anti-diarrheal therapy (e.g. loperamide). Patients with severe diarrhea should be closely monitored and given fluid and electrolyte replacement for dehydration as indicated. Dehydration may result in acute renal failure, particularly with other risk factors (preexisting renal dysfunction, concomitant nephrotoxic agents). Capecitabine should be held and the dose reduced after recovery. Older patients (≥ 65 years) may be at higher risk.

Palmar-plantar erythrodysesthesia (commonly referred to as hand-foot syndrome) is characterized by numbness, dysesthesia or paresthesia, tingling, painless or painful swelling, erythema, desquamation, blistering, and severe pain of the hands and/or feet and is more common in patients also receiving docetaxel. The median time to onset was 79 days. Dosage interruption/adjustment is required according to severity. In addition to dose interruption and subsequent dose reduction, topical emollients (e.g. hand creams, udder balm) may ameliorate the manifestations of hand-foot syndrome in patients receiving capecitabine. Current evidence indicates that oral pyridoxine may not be effective in ameliorating hand-foot syndrome in patients receiving capecitabine. (Kang 2010).

Severe rashes have been reported (Stevens-Johnson syndrome, Toxic Epidermal Necrolysis). Capecitabine must be permanently discontinued and the patient treated appropriately.

Hyperbilirubinemia associated with capecitabine therapy occurs more frequently in patients with hepatic metastases.

Patients with very low or absent dihydropyrimidine dehydrogenase (DPD) deficiency (ratelimiting enzyme of 5-fluorouracil catabolism) are at increased risk of severe or lifethreatening toxicity (i.e. neutropenia, GI and neurotoxicity, including fatalities) and should not receive capecitabine. In patients with partial DPD deficiency, capecitabine should be used with extreme caution, where the benefits outweigh the risks of treatment.

Cardiac toxicity is similar to that reported for other fluorinated pyrimidines and includes ECG changes, angina, infarction, EKG changes, dysrhythmias and cardiac failure. The risk may be increased in patients with prior coronary artery disease.

Very rare cases of leukoencephalopathy have been reported.

3.4.5 Pharmacokinetic Studies

It has 70% oral absorption reaching Cmax in 1.5 hours. Pharmacokinetics is largely dose proportional with insignificant food effect. The pharmacokinetics is altered with advanced age and renal function but nor with gender, race, performance status, liver function and albumin. It is widely distributed with less than 60% plasma protein binding, primary to albumin (35%). Capecitabine is extensively bioactivated and metabolized in the liver. Elimination is mainly in the urine (70%) with a terminal half-life of 45 – 60 mins.

3.4.6 Pharmaceutical Data

Refer to the package insert.

4.0 STUDY POPULATION

This study population includes patients with stage I-II (cT1-3^{ab}/N0) rectal cancer.

This study is designed to include women and minorities as appropriate, but is not designed to measure differences in intervention effects.

4.1 Eligibility Criteria

There will be NO EXCEPTIONS to eligibility requirements at the time of enrollment. Questions about eligibility criteria should be addressed prior to enrollment.

The eligibility criteria for this study have been carefully considered. Eligibility criteria are standards used to ensure that patients who enter this study are medically appropriate candidates for this therapy and to ensure that the results of this study can be useful for making treatment decisions regarding other patients with similar disease.

These eligibility criteria are expected to be followed. Any proposed variance must be discussed with CCTG prior to patient enrollment:

4.1.1 Histologically confirmed invasive well-moderately differentiated rectal adenocarcinoma diagnosed within 90 days prior to enrollment.

Note: it is recommended that surgeons take a biopsy of the tumour during sigmoidoscopy / colonoscopy to ensure tissue availability and adequate pathology report confirming invasive well-moderately differentiated rectal adenocarcinoma and no evidence of pathologic high risk factors.

4.1.2 Tumour stage cT1-T3^{ab}N0 based on pelvic MRI:

- cT1N0 – tumour invasion into submucosa, no radiographic evidence of mesorectal nodal metastasis, tumour deposits or vascular invasion.
- cT2N0 – tumour invasion into muscularis propria, no radiographic evidence of mesorectal nodal metastasis, tumour deposits or vascular invasion.
- cT3a,bN0 – tumour invasion through the muscularis propria no more than 5 mm into the subserosa/perirectal tissue and clear of the circumferential radial margin (CRM). Absence of radiographic evidence of mesorectal nodal metastasis, tumour deposits or lymphovascular invasion *[Glimelius 2010]*.

Note: If the tumour is not visualized in the MRI but there is histological confirmation of rectal adenocarcinoma the patient is eligible.

4.1.3 cN0 stage based on pelvic MRI. Any nodes ≥ 10 mm in longest dimension are considered malignant, regardless of nodal morphology. For pelvic nodes < 10 mm in longest dimension, if nodes are seen and are deemed to be morphologically benign in the opinion of the radiologist and surgeon, the patient is eligible. Patients with visible pelvic sidewall nodes are excluded.

4.1.4 M0 stage based on no evidence of metastatic disease by CT imaging.

4.1.5 Mid to low-lying tumour eligible for local tumour excision in the opinion of the treating surgeon.

4.1.6 Age of at least 18 years.

4.1.7 Medically fit to undergo radical surgery as per treating surgeon's discretion.

4.1.8 No contraindications to protocol chemotherapy.

4.1.9 Adequate normal organ and marrow function as defined below (must be done within 30 days prior to enrollment):

- ANC $\geq 1.5 \times 10^9/L$
- platelet count $\geq 100 \times 10^9/L$
- bilirubin $< 1.5 \text{ ULN}$, excluding Gilbert's syndrome
- Calculated creatinine clearance of $\geq 50 \text{ ml/min}$.
- Clearance to be calculated using Cockcroft formula:
Males:
$$\frac{1.23 \times (140 - \text{age}) \times \text{weight (kg)}}{\text{serum creatinine } (\mu\text{mol/l})}$$

Females:
$$\frac{1.05 \times (140 - \text{age}) \times \text{weight (kg)}}{\text{serum creatinine } (\mu\text{mol/l})}$$

4.1.10 The patient must have an ECOG performance status of 0, 1.

4.1.11 Patient is able (i.e. sufficiently fluent) and willing to complete the quality of life and health utility questionnaires. The baseline assessment must be completed within required timelines prior to enrollment. Inability (illiteracy, loss of sight, or other equivalent reason) to complete the questionnaires will not make the patient ineligible for the study. However, ability but unwillingness to complete the questionnaires will make the patient ineligible.

4.1.12 Patient consent must be appropriately obtained in accordance with applicable local and regulatory requirements. Each patient must sign a consent form prior to enrollment in the trial to document their willingness to participate.

4.1.13 Must be accessible for treatment and follow-up. Patients enrolled on this trial must be treated with chemotherapy and followed at the enrolling centre. This implies there must be reasonable geographical limits (for example: 1 ½ hour's driving distance) placed on patients being considered for this trial. The patient's city of residence may be required to verify their geographical proximity. (Call the CCTG office [contact]) if questions arise regarding the interpretation of this criterion.) Investigators must assure themselves the patients enrolled on this trial will be available for complete documentation of the treatment, adverse events, follow-up and response assessments.

Patients must agree to return to their primary care facility for any adverse events which may occur through the course of the trial.

4.1.14 Protocol treatment is to begin within 5 working days of patient enrollment.

4.1.15 Women/men of childbearing potential must have agreed to use a highly effective contraceptive method during and for 6 months after completion of chemotherapy. A woman is considered to be of "childbearing potential" if she has had menses at any time in the preceding 12 consecutive months. In addition to routine contraceptive methods, "effective contraception" also includes heterosexual celibacy and surgery intended to prevent pregnancy (or with a side-effect of pregnancy prevention) defined as a hysterectomy, bilateral oophorectomy or bilateral tubal ligation, or vasectomy/vasectomized partner. However, if at any point a previously celibate patient chooses to become heterosexually active during the time period for use of contraceptive measures outlined in the protocol, he/she is responsible for beginning contraceptive measures.

Women of childbearing potential will have a pregnancy test to determine eligibility as part of the Pre-Study Evaluation (see Section 5.0); this may include an ultrasound to rule-out pregnancy if a false-positive is suspected. For example, when beta-human chorionic gonadotropin is high and partner is vasectomized, it may be associated with tumour production of hCG, as seen with some cancers. Patient will be considered eligible if an ultrasound is negative for pregnancy.

4.2 Ineligibility Criteria

Patients who fulfill any of the following criteria are not eligible for admission to the study:

- 4.2.1 Patient has pathologic high risk factors on either the initial biopsy specimen report or follow up biopsy (if done): high histologic grade, mucinous histology, lymphatic or vascular invasion.
- 4.2.2 History of other malignancies, except: adequately treated non-melanoma skin cancer, curatively treated in-situ cancer of the cervix, or other solid tumours curatively treated with no evidence of disease for ≥ 5 years.
- 4.2.3 Synchronous cancer.
- 4.2.4 Prior treatment for rectal cancer.
- 4.2.5 Previous pelvic radiation for any reason.
- 4.2.6 Patients with known dihydropyrimidine dehydrogenase deficiency
- 4.2.7 Treatment with other investigational drugs or anti-cancer therapy within 28 days prior to enrollment.
- 4.2.8 Clinically significant (i.e. active) cardiovascular disease for example cerebro vascular accidents (< 6 months prior to enrollment), myocardial infarction (< 6 months prior to enrollment), unstable angina, New York Heart Association (NYHA) grade II or higher, congestive heart failure, serious cardiac arrhythmia requiring medication.
- 4.2.9 Any contra-indications to undergo MRI imaging.

5.0 PATIENT EVALUATION FLOWSHEET: PRE-TREATMENT, ON STUDY, AND AFTER TREATMENT

All patients entered on study must be evaluated according to the schedule outlined below with documentation submitted according to the schedule in Appendix II.

Required Investigations	Prior To Enrollment		During Protocol Treatment Prior to each FOLFOX or CAPOX cycle	Pre-Excision 2 weeks (FOLFOX) or 3 weeks (CAPOX) after last injection in last cycle of chemotherapy	Excision within 3 weeks after pre-excision visit	After Excision ¹		First Disease Relapse ²	After First Disease Relapse (Phone Contacts Acceptable) ³
	Within 90 days	Within 30 days				30 d	Months 6, 12, 18, 24, 30 and 36.		
History and Physical Exam									
Including: height (baseline only), weight, ECOG performance status		X	X ⁴	X		X	X		
Concomitant Medications		X	X ⁴	X	X	X			
Hematology									
CBC, differential (including lymphocytes), platelets		X	X ⁴	X					
Coagulation									
PTT, PT/INR		X		X					
Biochemistry									
ALT, serum creatinine, total bilirubin		X	X ⁴	X					
Creatinine Clearance (calculated)		X	X ⁴	X					
Serum CEA		X		X			X		
Correlative Studies									
Tumour tissue specimen banking ⁵	X				X				
Whole blood (for ctDNA), whole blood, serum and plasma ^{5, 6}		X		X		12, 24 and 36 ⁷		X ^{7, 8}	
Radiology									
MRI pelvis	X			X		6, 18 and 30 ⁷		X	
CT pelvis ⁹ (optional if pelvic MRI performed)	X					12, 24 and 36		X	
CT chest ⁹	X					12, 24 and 36		X	
CT abdomen with contrast ¹⁰	X					12, 24 and 36		X	
Sigmoidoscopy/Colonoscopy ¹¹	X			X		X ¹²		X	
Other Investigations									
Biopsy confirming invasive well-moderately differentiated rectal adenocarcinoma	X ¹³				X			X ¹⁴	
Pregnancy test ¹³		X							
Submission of tumour tissue for retrospective central yp staging confirmation (mandatory)					X				
Capecitabine patient diary			Daily ¹⁶						
Adverse Events									
Adverse event assessment ¹⁷		X	X	X	X	X	X ¹⁸	X ¹⁸	X ¹⁸

table continues on next page

Required Investigations	Prior To Enrollment		During Protocol Treatment Prior to each FOLFOX or CAPOX cycle	Pre-Excision 2 weeks (FOLFOX) or 3 weeks (CAPOX) after last injection in last cycle of chemotherapy	Excision within 3 weeks after pre-excision visit	After Excision ¹		First Disease Relapse ²	After First Disease Relapse (Phone Contacts Acceptable) ³
	Within 90 days	Within 30 days				30 d	Months 6, 12, 18, 24, 30 and 36		
Quality of Life									
EORTC QLQ-30 and EORTC QLQ-CR29		X		X			6, 12, 24 and 36		
LARS and the Fecal Incontinence Quality of Life Instrument		X		X			6, 12, 24 and 36		
Health Economics									
EQ-5D-5L		X	X ¹⁹	X		X	6, 12, 24 and 36		
Phone Contact									
Survival information								X	X
1. Timing for visits after excision are scheduled from last tumour excision date: a. For patients having TME as first protocol excision: from TME date b. For patients having TEMS/TAMIS as first protocol excision: from TEMS/TAMIS date c. For patients having TEMS/TAMIS as first protocol excision and then having a TME: from TME date 2. See protocol section 8 for definitions. 3. Phone contacts or visits after first disease relapse are required every 6 months from date of relapse. 4. Tests may be done on the date of treatment or, if not possible, the previous working day before treatment day. If treatment is to begin on a Monday, may be done on the previous Friday (maximum 72 hours prior to treatment). 5. Please also see protocol Section 12.0 and details for collection, processing, storing, and shipping these samples provided in the CO.28 Correlative Studies Manual. 6. Whole blood (that is not for ctDNA testing) will only be collected prior to enrollment. 7. Not required for patients that had a TME. 8. To be obtained within 28 days as close to the time of relapse as possible. Blood for correlatives done within 28 days PRIOR to date of relapse does not need to be repeated. 9. For CT pelvis and chest, a CT scan with contrast is preferred but not mandated. Patients with contrast allergies may undergo chest X-ray and /or Chest MRI. 10. Contrast is REQUIRED for the CT scan of the abdomen. Patients with contrast allergies may undergo liver ultrasound and /or MRI. 11. Rectal exam and proctoscopy are ideally to be performed by the primary surgeon. Proctoscopy should be performed ≤ 90 days prior to enrollment. Ideally, the surgeon should perform pre and post induction treatment proctoscopies. A gastroenterologist may perform proctoscopy in lieu of the surgeon, but then must also perform the follow-up exam. Proctoscopy may be accomplished using rigid proctoscopy or as part of a flexible sigmoidoscopy or colonoscopy. 12. For patients that had a TME it is only required at month 36. 13. If a rectal tumour tissue biopsy was performed within 90 days prior to enrollment, a repeat biopsy is not necessary. It is recommended that surgeons take a biopsy of the tumour during sigmoidoscopy/colonoscopy to ensure tissue availability and adequate pathology report confirming invasive well-moderately differentiated rectal adenocarcinoma and no evidence of pathologic high risk factors. 14. It is strongly encouraged that suspicious or unequivocal evidence of first local relapse be confirmed definitively by either biopsy (preferred) or by repeat/confirmatory imaging. Where imaging evidence of first local relapse is, in the opinion of the investigator and radiologist, absolutely unequivocal and not requiring subsequent confirmation by either biopsy or follow-up imaging, this must be clearly indicated in supporting documentation. 15. Urine pregnancy test in women of childbearing potential and if a false-positive is suspected this may include an ultrasound to rule-out pregnancy. 16. To be completed daily for patients receiving Capecitabine. 17. Adverse Events to be evaluated using the NCI Common Terminology Criteria for Adverse Events (CTCAE v5.0) (see Appendix III). 18. Only protocol chemotherapy or surgery related adverse events have to be reported after the 30 days post-excision visit. 19. After 3 cycles of FOLFOX or after 2 cycles of CAPOX.									

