1.2 Secondary Objectives

1. To describe the 3-year Locoregional Relapse Rate (LRR) in patients treated with organ preservation.
2. To describe the 3-year Distant Relapse Rate (DRR) in patients treated with organ preservation.
3. To describe the 3-year Disease Free Survival (DFS) rate in patients treated with organ preservation.
4. To evaluate the rate of post-operative complications following neoadjuvant FOLFOX/CAPOX and tumour excision/surgery.
5. To evaluate nature, severity and frequency of acute and long term toxicities in all patients.
6. To evaluate Quality of Life (QoL) in all patients.
7. To evaluate the cost-effectiveness of the neo-adjuvant chemotherapy approach vs. the current standard approach.

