7.2 Radiation Treatment Plan

Pelvic radiation is recommended for patients when the excisional specimen demonstrates ypT3+ or N+ disease and requires radical TME surgery. Patients should be treated with standard preoperative chemoradiation or short course pelvic radiation according to standard institutional pre-operative protocol.

Optional preoperative pelvic radiation could be delivered as per institution standard to patients with pre-excision MRI reporting at least one of these findings:

- cT3^{ab} stage
- node positive disease
- not clear circumferential radial margin (CRM)

Patients with yp staging as T1 (high risk) and T2 tumours do not require pre-operative pelvic radiation and should proceed directly to radical TME surgery.

Patients who cannot tolerate six cycles of FOLFOX or those that require dose modification below dose level -2 (see Section 7.1.3.1) may receive preoperative 5FU chemoradiotherapy based on investigator decision. If chemoradiotherapy is given, it should be given according to local institutional guidelines for FOLFOX administration.

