8.8 Management Following Relapse

Management following relapse is at the discretion of the investigator. Survival and protocol chemotherapy or surgery related adverse events data should continue to be capture after first relapse.

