7.8.1 Adverse Events

Adverse events (AEs) are recorded in the Adverse Events (AE) sections of CRF Chemotherapy Report, CRF Pre-Excision Report, CRF Surgery Report, CRF Follow Up Report (only AEs thought to be related to protocol treatment), and CRF Short Follow Up Report (ongoing or new grade 3 or higher AEs which are thought to be related to protocol treatment). Severity grade 5 will be combined with grade 4 for the purpose of this report. Adverse events reported during study treatment (in AE sections of CRF Chemotherapy Report, CRF Pre-Excision Report, and CRF Surgery Report) are defined as acute (on treatment) adverse events. Adverse events reported in AE section of CRF Follow Up Report and CRF Short Follow Up Report will be defined as delayed (long term) AEs.

Treatment (capecitabine, oxaliplatin, leucovorin, surgery, and radiotherapy) related adverse events are those events with a relation to protocol therapy of 3=possible,

4=probable or 5=definite.

Severe adverse events are those events reported with a NCI CTCAE Grade of 3 or higher.

The following variables are summarized:

- Acute adverse events: worst CTCAE grade per patient (**Table 32**)
- Severe acute adverse events: worst CTCAE grade per patient (**Table 33**)
- Treatment related acute adverse events: worst CTCAE grade per patient (**Table 34**)
- Delayed severe adverse events: worst CTCAE grade per patient (**Table 35**)

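### After the 30-day post-excision visit the protocol does not require adverse events attributed solely to its own pelvic radiotherapy, while the SAP counts radiotherapy-related events as treatment-related

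*Protocol*

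**What the plan says.** **Protocol, reporting rule.** Footnote 18 of the section 5.0 flowsheet reads: "Only protocol chemotherapy or surgery related adverse events have to be reported after the 30 days post-excision visit". It is attached to the adverse event row in all three later columns: the visits at months 6 to 36, first relapse, and after relapse. Section 8.8 says the same for the period after relapse: "Survival and protocol chemotherapy or surgery related adverse events data should continue to be capture after first relapse". Neither names radiotherapy.

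**Protocol, treatment plan.** Section 7.2: "Pelvic radiation is recommended for patients when the excisional specimen demonstrates ypT3+ or N+ disease and requires radical TME surgery". The same section adds: "Optional preoperative pelvic radiation could be delivered as per institution standard to patients with pre-excision MRI reporting at least one of these findings". It also allows chemoradiotherapy, at the investigator's decision, for patients who cannot tolerate the planned FOLFOX. The surgical table in section 7.3 carries the first two routes.

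**Protocol, objective.** Secondary objective 5: "To evaluate nature, severity and frequency of acute and long term toxicities in all patients". No treatment modality is singled out or left out.

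**SAP.** Section 7.8.1 gives as one source of events the "CRF Follow Up Report (only AEs thought to be related to protocol treatment"). The Short Follow Up Report adds related events of grade 3 or higher. Events from these two forms are what the SAP calls delayed. The attribution sentence begins: "Treatment (capecitabine, oxaliplatin, leucovorin, surgery, and radiotherapy) related adverse events are those events". The note under Table 34 plans a table of radiotherapy-related events, but Table 34 covers acute events. Table 35, the only delayed table, shows grade 3 and above without a split by modality.

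**The concern.** The two documents set different boundaries for the same data. The SAP expects follow-up events related to protocol treatment and counts radiotherapy as treatment. The protocol obliges sites to report only what is related to chemotherapy or surgery. A site that keeps to the protocol minimum need not send a month 12 event that it attributes to radiotherapy alone.

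The gap matters more here than it would elsewhere. Protocol section 2.0 justifies the strategy largely by the late harm of pelvic radiation to bowel, sphincter and sexual function. Patients who are irradiated in this trial are mostly those for whom organ preservation did not work out. If their late radiation toxicity is recorded less completely than other toxicity, the error runs in favour of the strategy. Objective 5 is the result affected.

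**Working it through.** The plan states no figure on this point, so there is nothing to reproduce. The check is a comparison of texts, followed by a rough scale calculation.

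**Step 1. Is radiotherapy protocol treatment?** Yes, on the documents' own usage. Sections 7.2 and 7.3 recommend or allow it. The disease-free survival table in section 8.7 counts non-protocol radiotherapy as a failure, which implies that there is also protocol radiotherapy. Appendix III starts the Follow-up Report once chemotherapy, radiotherapy and excision are complete. SAP 7.8.1 lists it among the treatments.

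**Step 2. Which events fall outside the requirement?** An event must meet both conditions:
- It occurs after the 30-day post-excision visit. Footnote 1 of the flowsheet sets the clock: "For patients having TEMS/TAMIS as first protocol excision and then having a TME: from TME date". Radiotherapy in sections 7.2 and 7.3 comes before TME, so for patients who reach TME, toxicity up to 30 days after that operation is inside the full reporting period.
- It is attributed to radiotherapy and not to chemotherapy or surgery. SAP 7.8.1 treats a relation graded as possible as related, so an event with surgery as a possible cause stays reportable.

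What is left is late toxicity attributed solely to radiotherapy.

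**Step 3. Does another route catch it?** Only in part.
- Section 9.1 sets no end date for expedited reports, but the event must be serious and unexpected against the product monograph, and relatedness refers to the protocol agent. That fits radiotherapy poorly.
- QLQ-CR29, LARS and FIQL at months 6, 12, 24 and 36 measure bowel, urinary, sexual and continence function whatever the cause, but give no CTCAE grade.
- SAP Tables 43 to 45 show follow-up endoscopy, transfusions and major medical problems with no attribution filter, but these are not graded adverse events.

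**Step 4. Scale.** SAP 2.2 gives 58 patients accrued. Neither the share irradiated (f) nor the rate of late grade 3+ radiotherapy events among them (q) is in the documents. Both ranges below are assumptions. The value f = 35% is 1 - 0.65, everyone not preserved at the target rate in protocol section 13.3.

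Patients missed = 58 × f × q. Understatement of the all-patient rate = f × q.

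| f | Irradiated (58 × f) | Missed, q = 5% | Missed, q = 20% | Understatement (points) |
|---|---|---|---|---|
| 5% | 2.9 | 0.1 | 0.6 | 0.25 to 1.0 |
| 20% | 11.6 | 0.6 | 2.3 | 1.0 to 4.0 |
| 35% | 20.3 | 1.0 | 4.1 | 1.75 to 7.0 |

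Every cell assumes that all such events are lost and that the patient has no other severe delayed event. Among irradiated patients only, the understatement would be q itself, 5 to 20 points. Table 35 uses chemotherapy-treated patients, whose number is not given; 58 is its maximum.

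**The case against.** The strongest reply is that this is a wording mismatch with little consequence. Several parts of it stand.

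- A reader might infer that late radiotherapy toxicity goes uncollected, or that sites are told not to send it. The documents do not support that. Footnote 18 states what must be reported, which is a minimum and not a ban. The SAP describes the follow-up forms more broadly than footnote 18. The forms themselves are not in the documents, so what sites entered is unknown.
- A reader might infer that delayed radiotherapy events are close to zero by rule. Steps 2 and 3 show otherwise: shared attribution with surgery keeps many late pelvic events reportable, and function is measured by questionnaire.
- A reader might infer that the comparison with standard care is biased. Protocol section 13.7 names efficacy data and EQ-5D-5L utilities as the trial's inputs to the cost-utility model. Utilities need no causal attribution, and Table 35 is not named as an input.
- The irradiated group may be small. Section 7.2 sends ypT2 and high-risk ypT1 patients to TME without radiation, and radiation after MRI non-response is optional.

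It can also be argued that the trial studies chemotherapy plus local excision, that radiation follows institutional practice, and that limiting late reporting to the studied components is a choice. That would be defensible if it were stated. But objective 5 covers all toxicities in all patients, and the SAP attributes events to radiotherapy, so the two documents do not make that choice together.

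**Conclusion.** The inconsistency is real and stands on the text alone. Read as written, the protocol does not require late events attributed solely to radiotherapy, although radiotherapy is in its treatment plan, objective 5 has no modality limit, and the SAP counts such events as treatment-related. Capture is therefore unreliable, and delayed severe toxicity in irradiated patients may be understated.

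The direction is plausible; the size is unknown. The scale table rests wholly on assumed inputs and on complete loss of these events, so its upper end is a deliberately unfavourable case within those inputs. The documents do not establish that any event was lost, or that the overall toxicity result is materially wrong. The point is worth correcting because any error would favour the strategy and the correction is cheap.

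**What to change.** 1. Reconcile footnote 18, section 8.8 and the follow-up forms with SAP 7.8.1 by naming protocol-directed radiotherapy beside chemotherapy and surgery. Radiotherapy given for a relapse need not be included.
2. Add a variant of SAP Table 35: delayed severe events related to radiotherapy, among patients who received it. The note under Table 34 already does this for acute events.
3. For data collected under the narrower rule, report the number of patients irradiated and state that late events attributed only to radiotherapy were not required. Table 29 as laid out will not give the full number: its data set is limited to patients who had TEMS or TAMIS, so it leaves out those irradiated after MRI non-response who went directly to TME. Count over all chemotherapy-treated patients.

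The cost is a short wording change in two protocol places and on the forms, a few more adverse event entries for irradiated patients, and one extra table. The visits and forms already exist, and no treatment rule changes.
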